18.4 Repeated or Unscheduled Assessments of Safety Parameters

Assessments will be mapped to analysis visit according to rules specified in Section 18.2. Additional repeated or unscheduled assessments will not be included in the by visit summary tables, but will be included in subject listings. Assessments that were not mapped to any analysis window (including repeated or unscheduled assessments) will be included in LOCF and modified WOCF imputation and subject listings.

18.5 Missing Date of Investigational Product

When the date of the last dose of investigational product is missing for a subject in the Safety Population, all efforts should be made to obtain the date from the investigator. If it is still missing after all efforts, then the last visit date when investigational product was returned will be used in the calculation of treatment duration.

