6.2.3 Dosing

Subjects will be instructed to instill 1 drop of investigational product in each eye QID (with a minimum of 2 hours between doses) for 7 days.

Prior to administration of the first dose, the bottle should be removed from refrigeration and allowed to come to room temperature. The bottle will not be refrigerated before subsequent administrations. Storage requirements are discussed in Section [6.3.3](#).

The investigational product bottle should be shaken well prior to use at each dosing.

In-office dosing will only be performed at the first visit, and additionally if necessary.

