- Dispense and instill investigational product in both eyes by the designated site staff investigational product administrator. The investigational product bottle should be shaken well prior to use at each dosing.

All assessments, randomization, and investigational product instillation on Day 1 must take place with sufficient time to allow all 4 Day 1 doses (with a minimum of 2 hours between doses).

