2.4 Schedule of Assessments

Table 1 below presents the schedule of assessments.

Table 1 Schedule of Assessments

| Procedure (All ocular assessments and procedures performed bilaterally) | Visit 1 Screening ^a and Baseline (Day 1) -1 Day | Visit 2 (Day 3) +1 Day | Visit 3 (Day 5) | Visit 4 (Day 8) +1 Day | Visit 5 ^b (Day 12) +2 Days |
|---|--|------------------------------|--------------------|------------------------------|---|
| Informed consent/assent ^a | X | | | | |
| Inclusion/exclusion criteria ^a | X | | | | |
| Medical history | X | | | | |
| Demographics | X | | | | |
| Concomitant medications | X | X | X | X | X |
| Urine pregnancy test | X ^c | | | | X ^c |
| Ocular discomfort scale | X | X | X | X | X |
| Best corrected visual acuity | X | X | X | X | X |
| Slit lamp biomicroscopy | X | X | X | X | X |
| Bulbar conjunctival injection evaluation | X | X | X | X | X |
| Ocular conjunctival discharge evaluation | X | X | X | X | X |
| AdenoPlus [®] test | X ^d | | | | |
| Conjunctival swab for bacterial culture ^e | X | X ^f | X ^f | X ^f | X |
| Conjunctival swab to test for HSV, and chlamydia and gonorrhea ^l | X | | | | |
| Non-dilated/dilated fundus examination ^k | X | | | | X |
| Randomization ^g | X | | | | |
| Dispense investigational product ^h | X | | | | |
| Instill investigational product | X ^h | X ⁱ | X ⁱ | | |
| Collect investigational product | | | | X | X ^b |
| Compliance assessment | | X | X | X | X ^b |
| Drug accountability | | | | X | X ^b |
| Adverse events | X ^j | X | X | X | X |
| Study completion | | | | | X |

ET=early termination;

^a Informed consent and confirmation of inclusion/exclusion criteria can be conducted on Day -1; these criteria must be reconfirmed on Day 1.

^b If investigational product is discontinued, regardless of the reason, all discontinued subjects should proceed to Visit 5 whenever possible. Subjects who discontinue the study and proceed to Visit 5 should perform all Visit 5 assessments as well as drug return, compliance, and accountability.

^c Women of childbearing potential, prior to enrollment and at exit from the study

^d If not previously conducted within 24 hours of Visit 1 (Day 1)

^e One swab sample from inferior conjunctival cul-de-sac of each eye will be collected for all bacterial testing.

^f Conjunctival swab samples MUST be taken at least 12 hours after the last dose of investigational product at Visits 2, 3, 4, and ET, if applicable.

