8. EXTENT OF EXPOSURE AND TREATMENT COMPLIANCE

8.1 Exposure to Investigational product

Exposure to double-masked investigational product for the Safety Population will be summarized in terms of treatment duration, which is calculated as the number of days from the date of first dose of double-masked investigational product taken to the date of the last dose of double-masked investigational product taken, inclusively, and irrespective of any investigational product interruption(s). Descriptive statistics will be presented by treatment group and overall.

A listing of investigational product exposure will be provided for all subjects in the Safety Population.

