8.2 Measurement of Treatment Compliance

Investigational product dosing compliance for the double masked treatment period is defined as the total number of doses actually taken by a subject during that period divided by the number of doses expected to be taken during the same period multiplied by 100.

For completers (i.e. subjects who completed all 7 days of dosing), the total number of expected doses is 28 (i.e. 4 doses per day for 7 days). For subjects who early terminated dosing on Day 1, the total number of expected doses is set to be 1. For the rest of subjects who terminated dosing before 7 days, the total number of expected doses is the number of full dosing day multiplied by 4. For example, if a subject early terminates on Day 4, his/her total number of expected doses is 3 (full dosing day) x 4 (doses per day) = 12.

At each visit, the number of missed doses or extra doses since last visit will be recorded on the CRF. The total number of missed doses will be derived as the sum of the number of missed doses since last visit across all visits. The total number of extra doses will be derived as the sum of the number of extra doses since last visit across all visits. The total number of doses actually taken will be derived as the total number of expected doses plus the total number of extra doses minus the total number of missed doses.

Descriptive statistics [number of subjects (n), mean, median, standard deviation (SD), minimum, maximum] for investigational product compliance will be presented by treatment group and overall for the whole double-masked evaluation phase for the Safety Population. Number of subjects (percentage) who completed 4 days of dosing by Visit 3 with no extra or missed dose will also be presented by treatment group and overall for the Safety Population.

A listing of treatment compliance will be provided for all subjects in the Safety Population.

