18.2 Study Visits and Windows

Assessments will be assigned to visits based upon the date the assessment took place regardless of the CRF page completed. Assessments will be mapped to visits as outlined in [Table 2](#).

Should there be more than 1 assessment mapped into a given study visit, the assessment closest to the planned visit will be used for analysis (referred to as analysis visit); if equally close, choose assessment obtained on the scheduled visit or the last assessment if there is no data on the scheduled visit.

Study day will be calculated as follows:

- If the assessment date is on or after the date of first instillation:

$$\text{Study day} = \text{assessment date} - \text{first dosing date} + 1$$

- If the assessment date is before the date of first instillation:

$$\text{Study day} = \text{assessment date} - \text{first dosing date}$$

Table 2: Visit Windows (Study Day Based)

| Visit | Planned Study Day | Start Day of Window | End Day of Window |
|--------------------------------|-------------------|---------------------|-------------------|
| Visit 1 (Screening & Baseline) | 1 | Date of CRF Visit 1 | 1 |
| Visit 2 | 3 | 3 | 4 |
| Visit 3 | 5 | 5 | 6 |
| Visit 4 | 8 | 8 | 9 |
| Visit 5 | 12 | 12 | 14 |

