18.6.2 Incomplete Stop Date

The following rules will be applied to impute the missing numerical fields. If the date of the last dose of investigational product is missing, then replace it with the last visit date. If the imputed stop date is before the start date (imputed or non-imputed start date), then the imputed stop date will be equal to the start date.

Missing day and month

- If the year of the incomplete stop date is the same as the year as of the date of the last dose of investigational product, then the day and month of the date of the last dose of investigational product will be assigned to the missing fields
- If the year of the incomplete stop date is before the year of the date of the last dose of investigational product, then 31 December will be assigned to the missing fields
- If the year of the incomplete stop date is after the year of the date of the last dose of investigational product, then 01 January will be assigned to the missing fields.

Missing month only

- The day will be treated as missing and both month and day will be replaced according to the above procedure.

Missing day only

- If the month and year of the incomplete stop date are the same as the month and year of the date of the last dose of investigational product, then the day of the date of the last dose of investigational product will be assigned to the missing day
- If either the year is before the year of the date of the last dose of investigational product or if both years are the same but the month is before the month of the date of the last dose of investigational product, then the last day of the month will be assigned to the missing day
- If either the year is after the year of the last dose of investigational product or if both years are the same but the month is after the month of the date of the last dose of investigational product, then the first day of the month will be assigned to the missing day.

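### SAP 18.5 replaces a missing last-dose date with the product-return visit date and sets no cap at Day 7, so returns at Visit 4 or on Days 12 to 14 give durations longer than the 7-day regimen

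*SAP*

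**What the plan says.** **Regimen.** Protocol 6.2.3 has subjects instil one drop "in each eye QID (with a minimum of 2 hours between doses) for 7 days". Protocol 7.1.1 makes Day 1 a full dosing day: the Visit 1 procedures "must take place with sufficient time to allow all 4 Day 1 doses". For a subject who completes dosing, SAP 8.2 states that "the total number of expected doses is 28 (i.e. 4 doses per day for 7 days").

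**Duration.** SAP 8.1 counts from the first-dose date "to the date of the last dose of double-masked investigational product taken, inclusively", and ignores interruptions.

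**Missing last-dose date.** SAP 18.5 first requires that the date be sought from the investigator. If that fails, "the last visit date when investigational product was returned will be used in the calculation of treatment duration".

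**When product comes back.** The schedule in SAP 2.4 has the row "Collect investigational product | | | | X | X ^b", which places collection at Visit 4 and, under footnote b (discontinued subjects), at Visit 5. SAP Table 2 gives Visit 4 a window of Day 8 to 9. Its Visit 5 row is "Visit 5 | 12 | 12 | 14", a window of Day 12 to 14.

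**A second rule for the same date.** SAP 18.6.2, on partial stop dates of other medications, says: "If the date of the last dose of investigational product is missing, then replace it with the last visit date".

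**The concern.** The return visit is an administrative date that normally falls after dosing has ended. Protocol 7.1.2 tells subjects not to dose in the 12 hours before Visits 2, 3 and 4, and the schedule marks in-office instillation only at Visits 1 to 3. A compliant subject who hands the bottle back at Visit 4 would therefore ordinarily not have dosed that day. Even so, SAP 18.5 treats it as the last dosing day.

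One imputed subject is enough to show. SAP 18.1 reports minimum and maximum for continuous variables, so Table 14.3.8.1 could give a maximum of 14 days for a 7-day regimen. Listing 16.2.5.3, which combines exposure and compliance, could show 14 days of exposure beside 28 expected doses. SAP 9 and 11.1 have imputed dates marked in the medication and adverse event listings, but SAP 8.1 says nothing of the kind for exposure.

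Separately, SAP 18.5 and 18.6.2 fill the same missing value with two different dates.

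**Working it through.** **Inputs**
- First dose on Day 1, four doses a day, 7 days (Protocol 6.2.3, 7.1.1).
- 28 expected doses for a completer (SAP 8.2).
- Duration = last-dose day − first-dose day + 1 (SAP 8.1).
- Visit 4 window Day 8 to 9; Visit 5 window Day 12 to 14 (SAP Table 2).

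**Step 1. Reproduce the plan's figure.** A last dose on Day 7 gives 7 − 1 + 1 = 7 days, and 7 × 4 = 28 doses. This matches SAP 8.2, so the planned maximum is 7 days.

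**Step 2. Apply SAP 18.5 to each possible return day.**

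| Return visit | Return day | Imputed duration | Compared with 7 days |
|---|---|---|---|
| Early termination before Day 8 | 2 to 7 | 2 to 7 days | not above 7 |
| Visit 4 | 8 | 8 days | +1 (8/7: +14%) |
| Visit 4 | 9 | 9 days | +2 (9/7: +29%) |
| Visit 5 on schedule | 12 | 12 days | +5 (12/7: +71%) |
| Visit 5 on schedule | 14 | 14 days | +7 (14/7: +100%) |

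The percentages are the error for a subject who really dosed through Day 7.

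**Step 3. An early stopper (illustration).** A subject who stopped on Day 3 and returned the bottle at Visit 4 would be given 8 to 9 days against 3, an excess of 5 to 6 days.

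**Step 4. Shift in an arm mean.** The documents give no rate of missing last-dose dates. Assume that 1% to 10% of an arm is imputed and that all of these subjects last dosed on Day 7. Shift = share imputed × excess days.
- Visit 4 returns: 0.01 × 1 = 0.01 to 0.10 × 2 = 0.20 days.
- Day 12 to 14 returns: 0.01 × 5 = 0.05 to 0.10 × 7 = 0.70 days.

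**Step 5. The two substitute dates.** Take a subject who returns product at Visit 4 and completes Visit 5 on schedule. SAP 18.5 gives Day 8 to 9 and SAP 18.6.2 gives Day 12 to 14. The gap is 12 − 9 = 3 to 14 − 8 = 6 days.

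**Step 6. Sensitivity to one wording.** Schedule footnote h has the first dose on Day 1 and dosing thereafter for 7 days. Read literally, the last dose could fall on Day 8, a maximum of 8 − 1 + 1 = 8 days. A Day 8 return would then not exceed it. A Day 9 return would exceed it by 1 day, and Day 12 to 14 returns by 4 to 6 days. The 28-dose count and the four Day 1 doses agree with Day 7. The footnote should be reconciled with them.

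**The case against.** The case for leaving the rule alone has several parts.

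- **Returns are not always late.** Discontinued subjects go to Visit 5 as an early-termination visit where product is collected (Protocol 7.1.3). In the rescue case that visit takes place when the subject discontinues (Protocol 4.4). A reader might infer that every imputed duration exceeds 7 days. The documents do not support that, although an early-termination return can still overstate true exposure. This part stands.
- **The largest errors need unusual paths.** Completers return product at Visit 4. The Visit 5 collection is footnoted to discontinued subjects, who are sent there rather than to Visit 4. So a 7-day user returning on Day 12 to 14, or a Day 3 stopper returning at Visit 4, departs from the usual schedule. Such cases remain possible: subjects with a positive baseline HSV test stop product but are followed at the scheduled visits (Protocol 4.4). The 8 to 9 day result needs no departure.
- **The date should seldom be missing.** Protocol 4.4 requires the stopping date in the CRF and source documents, and SAP 18.5 applies only as a last resort. This limits how often the rule is used, but does not change the value it gives.
- **Tolerability conclusions are not shown to change.** It is tempting to say that the rule distorts the safety assessment. SAP 18.5 confines the imputed date to treatment duration, SAP 11.1 defines treatment-emergent events by onset after the first dose, and SAP 11 plans no exposure-adjusted rates.
- **SAP 18.6.2 does not create a treatment end date.** It uses the last visit only as an anchor for partial stop dates of other medications. A reader might infer that the exposure and medication listings would print conflicting treatment end dates, but the text does not say so. What stands is that one missing value has two substitutes.

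**Conclusion.** The point holds as a minor data-handling defect. For a return at Visit 4, SAP 18.5 gives 8 to 9 days, and for a return on Day 12 to 14 it gives 12 to 14 days, against a planned maximum of 7. Returns before Day 8 do not exceed the maximum.

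The conclusion rests on dosing ending on Day 7, as the plan's own 28-dose count implies. Under the literal reading of footnote h, only the Day 8 result drops out.

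The consequences are confined to descriptive exposure summaries, most visibly the reported maximum, and to medication stop dates completed under SAP 18.6.2. The primary and key secondary tests do not use this date. The number of affected subjects is unknown and probably small, and the arm-mean shifts shown depend on an assumed 1% to 10% imputation rate.

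**What to change.** - **SAP 18.5:** impute the last-dose date as the earlier of the product-return visit date and study Day 7, unless dosing records show dosing after Day 7. The exception keeps genuine late dosing visible.
- **SAP 18.6.2:** use the same imputed date in place of the last visit date.
- **Listing 16.2.5.3:** flag the date as imputed.

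With the cap, Visit 4 returns fall from 8 to 9 days to 7, Day 12 to 14 returns fall from 12 to 14 days to 7, and early-termination returns on Days 2 to 7 do not change.

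The cap should not be tightened to the last day on which dosing was confirmed at a visit. SAP 8.2 records counts of missed and extra doses since the previous visit, not a last-dosed day. If Visit 3 were the last check, a full 7-day user could be cut to about 5 days.

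The cost is two SAP sentences and a listing flag, with no new data and no change to observed dates. Exposure in the few affected subjects will be reported as slightly shorter. The cap does not fully correct an early stopper: the Day 3 example would be given 7 days, still 4 too many, which is one reason to flag the value.

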18.6 Missing Date Information for Prior or Concomitant Medications

For prior or concomitant medications, including rescue medications, incomplete (ie, partially missing) start date and/or stop date will be imputed. When the start date and the stop date are both incomplete for a subject, impute the start date first.

18.6.1 Incomplete Start Date

The following rules will be applied to impute the missing numerical fields. If the stop date is complete and the imputed start date is after the stop date, then the start date will be imputed using the stop date.

Missing day and month

- If the year of the incomplete start date is the same as the year of the date of the first dose of investigational product, then the day and month of the date of the first dose of investigational product will be assigned to the missing fields
- If the year of the incomplete start date is before the year of the date of the first dose of investigational product, then December 31 will be assigned to the missing fields
- If the year of the incomplete start date is after the year of the date of the first dose of investigational product, then 01 January will be assigned to the missing fields.

Missing month only

- The day will be treated as missing and both month and day will be replaced according to the above procedure.

Missing day only

- If the month and year of the incomplete start date are the same as the month and year of the date of the first dose of investigational product, then the day of the date of the first dose of investigational product will be assigned to the missing day
- If either the year is before the year of the date of the first dose of investigational product or if both years are the same but the month is before the month of the date of the first dose of investigational product, then the last day of the month will be assigned to the missing day
- If either the year is after the year of the date of the first dose of investigational product or if both years are the same but the month is after the month of the date of the first dose of investigational product, then the first day of the month will be assigned to the missing day.

18.6.2 Incomplete Stop Date

The following rules will be applied to impute the missing numerical fields. If the date of the last dose of investigational product is missing, then replace it with the last visit date. If the imputed stop date is before the start date (imputed or non-imputed start date), then the imputed stop date will be equal to the start date.

Missing day and month

- If the year of the incomplete stop date is the same as the year as of the date of the last dose of investigational product, then the day and month of the date of the last dose of investigational product will be assigned to the missing fields
- If the year of the incomplete stop date is before the year of the date of the last dose of investigational product, then 31 December will be assigned to the missing fields
- If the year of the incomplete stop date is after the year of the date of the last dose of investigational product, then 01 January will be assigned to the missing fields.

Missing month only

- The day will be treated as missing and both month and day will be replaced according to the above procedure.

Missing day only

- If the month and year of the incomplete stop date are the same as the month and year of the date of the last dose of investigational product, then the day of the date of the last dose of investigational product will be assigned to the missing day
- If either the year is before the year of the date of the last dose of investigational product or if both years are the same but the month is before the month of the date of the last dose of investigational product, then the last day of the month will be assigned to the missing day
- If either the year is after the year of the last dose of investigational product or if both years are the same but the month is after the month of the date of the last dose of investigational product, then the first day of the month will be assigned to the missing day.

18.7 Missing Date Information for Adverse Events

For AEs, incomplete (i.e. partially missing) start dates will be imputed if the subject is missing whether the event occurred prior to the first study drug dose. Incomplete stop dates will not be imputed.

18.7.1 Incomplete Start Date

If incomplete start date needs to be imputed, then follow same rules as in Section [18.6.1](#).

18.8 Missing Severity Assessment for Adverse Events

If severity is missing for an AE starting prior to the date of the first dose of investigational product, then a severity of “Mild” will be assigned. If the severity is missing for an AE starting after the first dose of investigational product, then a severity of “Severe” will be assigned. The imputed values for severity assessment will be used for incidence summaries, while both the actual and imputed values will be used in data listings.

18.9 Missing Relationship to Investigation Product for Adverse Events

If the relationship to investigational product is missing for an AE starting after the first dose of investigational product, a causality of “Related” will be assigned. The imputed values for relationship to double-masked investigational product will be used for incidence summaries, while both the actual and imputed values will be presented in data listings.

